2.4 Nitric Oxide Pathway and Cancer Risk

In the past, there has been concern of the effect of exposure to dietary nitrates and nitrites and an increased risk of cancer. Indeed, the presence of nitrates and nitrites in food has been associated with an increased risk of gastrointestinal cancer in studies, predominantly the consumption of cured and processed meats (15). While associations of general dietary nitrite and nitrate consumption and cancer have guided the World Health Organization and others to recommend caution in ingestion, direct evidence of the negative effect on human carcinogenesis is lacking, despite extensive epidemiologic study (16). In addition, animal toxicological studies (17) have not conclusively established a relationship between nitrite exposure and the risk of cancer (18). The permissible concentration of nitrate in drinking water is 44 mg/L in the United States following World Health Organization recommendations 1970 and reaffirmed in 2004. More recent reviews have suggested a difference in nitrite and nitrate exposure from fruits and vegetables which are generally reported as beneficial to cardiovascular health and exercise tolerance. (19-21) In one recent review, Bryan et al, concluded that there is no significant correlation between nitrite or nitrate ingestion and gastric cancer risk (20, 22).

2.5 Rationale

The objective of the current proposal is to obtain pilot data to determine if concentrated beet root could potentially improve medical treatment compliance as defined by completion of radiotherapy or radiotherapy plus chemotherapy without dose reduction (primary outcome), and preserve fat-free mass, and strength while reducing mucositis (secondary outcomes). Our central hypothesis is that dietary nitrate/nitrite supplementation in head and neck cancer patients receiving aggressive medical care will improve compliance with medical treatment by attenuating the loss of muscle mass and strength and reducing symptoms (mucositis) associated with treatment compared to patients who do not receive dietary nitrate/nitrite supplementation. The rationale for this hypothesis is based on recent evidence that dietary nitrate supplementation improves measures of muscle strength, endurance, and performance capacity and the role nitrate may play in interrupting mucositis pathogenesis. Our long-term goal is to identify novel, nutrition intervention strategies to effectively reduce the negative side effects associated with chemotherapy and radiation that often impact therapeutic outcomes. Improvements in these outcomes will have a significant impact on augmenting the delivery of combined modal therapy and will contribute to improved quality of life.

Our working hypothesis is that beetroot supplementation will enable head and neck cancer patients to improve treatment compliance as defined by completion of radiotherapy or radiotherapy plus concurrent chemotherapy without dose reduction as compared to historic controls. The rationale for improved treatment compliance is based on expected improvements in strength, endurance and mucositis symptoms following beetroot treatment. These improvements are hypothesized to be greater in a head and neck cancer patient population presumed to be nitrate deficient.

3. PATIENT SELECTION

3.1 Eligibility Criteria

3.1.1 Patients must have a histologically confirmed malignancy of the head and neck (nasopharynx, oral cavity, oropharynx, hypopharynx, larynx, sinuses, skin or salivary gland) without distant metastatic disease and be planned to receive a continuous course of conventional external beam irradiation to at least 55 Gy of radiation to at least 2 mucosal sites with or without chemotherapy. Patients may have received induction therapy prior to definitive therapy for the current head and neck cancer.

3.1.2 Patients may have a history of prior malignancy, but must be able to tolerate full dose radiation and chemotherapy for the current head and neck cancer, as determined by the treating oncologist.

3.1.3 Age \geq 18 years.

3.1.4 ECOG performance status \leq 2, see Appendix A.

3.1.5 Life expectancy of greater than 3 months

3.1.6 Patients must have normal organ and marrow function as defined below:

- leukocytes	\geq 3,000/mcL
- absolute neutrophil count	\geq 1,500/mcL
- platelets	\geq 100,000/mcL
- total bilirubin	\leq 1.5 times ULN (upper limit of normal)
- ALT and AST	\leq 2.5 times the ULN
- Creatinine	\leq 1.5 times ULN

OR

- Measured creatinine clearance $>$ 60 mL/min

3.1.7 Able to swallow thin liquids or have a feeding tube for delivery of nutrition.

3.1.8 No uncontrolled illness including, but not limited to, any of the following:

- Ongoing or active serious infection
- Symptomatic congestive heart failure
- Unstable angina pectoris
- Uncontrolled cardiac arrhythmia
- Uncontrolled hypertension
- Psychiatric illness or social situation that would preclude compliance with study requirements

3.1.9 No other concurrent anticancer therapies or agents.

3.1.10 The effects of beet root on the developing human fetus are unknown. For this reason and because the subjects will be undergoing radiation and chemotherapy, women of child-bearing potential and men must agree to use adequate contraception (hormonal or barrier method of birth control; abstinence) prior to study entry and for the duration of study participation. Should a woman become pregnant or suspect she is pregnant while she or her partner is participating in this study, she should inform her treating physician immediately. Men treated or enrolled on this protocol must also agree to use adequate contraception prior to the study, for the duration of study participation, and 4 months after completion of beet root administration.

3.1.11 Ability to understand and the willingness to sign a written informed consent document.

3.2 Exclusion Criteria

3.2.1 Active infection > CTCAE Grade 2, that is considered clinically serious by the treating physician.

3.2.2 Pregnant women are excluded from this study because chemo-radiation has the potential for teratogenic or abortifacient effects. Because there is an unknown but potential risk for adverse events in nursing infants secondary to treatment of the mother with chemo-radiation, breastfeeding should be discontinued.

3.2.3 While there are no well documented drug-beet root juice interactions, HIV-positive patients on combination antiretroviral therapy are ineligible because of the potential for pharmacokinetic interactions with these drugs and beet root juice.

3.2.4 Subjects with a history of calcium oxalate nephrolithiasis are excluded.

3.2.5 Subjects with a significant history of malabsorption (e.g. celiac sprue, short bowel syndrome, or other, as determined by the treating physician) are excluded.

3.3 Inclusion of Women and Minorities

Both men and women of all races and ethnic groups are eligible for this trial. This study was designed to include women and minorities, but was not designed to measure differences of intervention effects. Men and women will be recruited with no preference to gender. No exclusion to this study will be based on race. Minorities will be actively recruited to participate.

Accrual Targets					
Ethnic Category	Sex/Gender				
	Females		Males		Total
Hispanic or Latino	0	+	1	=	1
Not Hispanic or Latino	8	+	26	=	34
Ethnic Category: Total of all subjects	8	+	27	=	35
	(A1)				(C1)

Racial Category					
American Indian or Alaskan Native	0	+	0	=	0
Asian	0	+	1	=	1
Black or African American	1	+	2	=	3
Native Hawaiian or other Pacific Islander	0	+	0	=	0
White	7	+	24	=	31
Racial Category: Total of all subjects	8	+	27	=	35
	(A2)		(B2)		

4. REGISTRATION PROCEDURES

4.1 Protocol Review and Monitoring Committee and Institutional Review Board Review

Before implementing this study, the protocol, the proposed informed consent form and other information to subjects, must be reviewed by the Markey Cancer Center's Protocol Review and Monitoring Committee and the University of Kentucky Institutional Review Board (IRB). A signed and dated statement that the protocol and informed consent have been approved by the IRB must be maintained in the Markey Cancer Center Clinical Research Organization (MCC CRO) regulatory binder. Any amendments to the protocol, other than administrative ones, must be reviewed and approved by the PRMC, study sponsor and the UK IRB.

4.2 Enrollment Guidelines

Eligible patients will be identified by the principal investigator and co-investigators of this study. Potentially eligible patients will be screened in the University of Kentucky Markey Cancer Center clinics by the investigators and study personnel. Upon obtaining proper consent, patients will be enrolled into the study.

4.3 Informed Consent

The goal of the informed consent *process* is to provide people with sufficient information so they can make informed choices about whether to begin or continue participation in clinical research. The process involves a dynamic and continuing exchange of information between the research team and the participant throughout the research experience. It includes discussion of the study's purpose, research procedures, risks and potential benefits, and the voluntary nature of participation.

The informed consent *document* provides a summary of the clinical study and the individual's rights as a research participant. The document acts as a starting point for the necessary exchange of information between the investigator and potential research participant. Also, research participants and their families may use the consent document as an information resource and reference throughout participation in the trial. The informed consent *document* is often considered the foundation of the informed consent process; it does not, however, represent the entirety of the process. Nor is the informed consent document a risk-management tool for the investigator and/or institution.

The investigator must explain to each subject (or legally authorized representative) the nature of the study, its purpose, the procedures involved, the expected duration, the potential risks and benefits involved and any discomfort it may entail. Each subject must be informed that participation in the study is voluntary and that he/she may withdraw from the study at any time and that withdrawal of consent will not affect his/her subsequent medical treatment or relationship with the treating physician.

This informed consent should be given by means of a standard written statement, written in non-technical language. The subject should read and consider the statement before signing and dating it, and should be given a copy of the signed document. If the subject cannot read or sign the documents, oral presentation may be made or signature given by the subject's legally appointed representative, if witnessed by a person not involved in the study, mentioning that the patient could not read or sign the documents. No patient can enter the study before his/her informed consent has been obtained. The informed consent form is considered to be part of the protocol, and must be submitted by the investigator with the protocol at the time of IRB review.

4.4 Compliance with Laws and Regulations

The study will be conducted in accordance with U.S. Food and Drug Administration (FDA) and International Conference on Harmonization (ICH) Guidelines for Good Clinical Practice (GCP), the Declaration of Helsinki, any applicable local health authority, and Institutional Review Board (IRB) requirements. The PI or designee will be responsible for obtaining continuing and not less than annual IRB re-approval throughout the duration of the study. Copies of the Investigator's annual report to the IRB and copies of the IRB continuance of approval must be maintained by the MCC CRO. The PI or designee is also responsible for notifying the Data and Safety Monitoring Committee of the MCC and the UK IRB of any significant adverse events that are serious and/or unexpected, as per SOP's of those entities. The MCC DSMC will review all adverse events of this IIT as per its SOP.]

5. TREATMENT PLAN

This is a non-randomized, pilot Phase II clinical trial that will determine the safety of concentrated beet root given in conjunction with radiation or radiation plus chemotherapy for locally advanced head and neck cancer. This trial will enroll 25 subjects taking beetroot supplement with up to an additional 10 standard of care subjects that refuse participation in the beetroot supplementation but are willing to obtain strength outcomes during their cancer treatment for a maximum of 35 patients.

5.1 Standard of Care Treatment Administration

All treatment will be administered on an outpatient basis. Adult subjects with head and neck cancer who are planned to receive a continuous course of conventional external beam irradiation delivered by intensity-modulated radiotherapy (IMRT) as single daily fractions of 2.0 to 2.2 Gy, to a minimum cumulative radiation dose of 55 Gy to at least 2 mucosal will be recruited through Markey Cancer Center to undergo screening and testing. Approximately a 3:1 ratio of males to females will be recruited based on reported cases of head and neck cancer, although no preference will be given to either sex. Based on Kentucky's ethnicity statistics, we expect to have a Caucasian: African American ratio of 9:1, as ethnicity and race are not exclusion criteria. The population is readily accessible from this resource. We plan to

enroll patients who are primarily fed enterally by a percutaneous endoscopic gastrostomy (PEG) tube. Patients on “po” diets with thin (standard consistency) liquids are also eligible. [name] will initially identify patients who are eligible based on the aforementioned criteria. A research associate will then explain the study to eligible participants and provide a research flier. Interested volunteers will then complete the formal consenting process prior to participation with the research associate under the direction of Drs. [name] and [name].

5.1.1 Radiation Therapy

All radiation therapy is considered standard of care, and toxicities and dose modifications will be made by the treating physician based on institutional standards. The guidelines below are recommended practice but may be modified at the discretion of the treating radiation oncologist.

5.1.1.1 Dose Specifications

IMRT has been a standard of care in the U.S. beginning in 2005 and is now widely used in practice. Use of H&N IMRT in RTOG protocols (and associated QA) was begun in 2005 in RTOG 0522, as an optional technique. At the close of the accrual phase, approximately 90% of cases enrolled on 0522 (>800 patients) were treated with IMRT. Oropharynx cases comprised 70% of the study population.

IMRT will be delivered in 30-35 fractions over 6-7 weeks, 5 fractions weekly. The primary tumor and involved nodes (CTV1) will typically consist of a 0.5-1.5 cm expansion of the gross tumor volume (GTV) to cover potential local invasion and will be prescribed 2 Gy/fraction, total 55-70 Gy. High-risk sub-clinical disease sites, which include possible local subclinical infiltration at the primary site (primary site CTV2) and first echelon nodes, which are not clinically or radiographically involved (nodal CTV2), should be expanded by 3-5 mm to create PTV2. PTV2 should receive 1.6 Gy/fraction to a total dose of 52.8 Gy to 56 Gy. Lower-risk targets (PTV3) (such as neck nodal levels which are not first echelon nodes and are not adjacent to levels containing grossly involved nodes) will be prescribed 50-52.5 Gy. If the low neck is treated, the preferred technique is to treat with isocentric matching AP or AP-PA fields with larynx block, matched to the IMRT portals just above the arytenoids. The dose will be 2 Gy per fraction prescribed to 3 cm depth to a total dose of 50 Gy in 25 daily fractions. Whole-neck IMRT is allowed. This can be achieved by either boosting the low neck field with an additional 16 Gy in 8 fractions, by an AP or AP-PA fields, or by planning the whole neck using IMRT. In cases of gross involvement of the vallecula or low neck, whole-neck IMRT should be considered. Whole-neck IMRT may also be considered if level VI is considered to be at risk due to gross involvement of level IV nodes. All plans must be normalized such that 95% of the volume of the PTV is covered with prescription dose..

In cases of weight loss > 10% or significant shrinkage of lymphadenopathy during therapy, it is recommended that the immobilization mask will be adjusted or re-made in order to preserve adequate immobilization, and that a repeated simulation CT be performed to assess the dose distributions in the current anatomy. Whether or not a new IMRT plan will be generated is at the discretion of the treating physician. If a new plan is made, the targets should be the same as those used for the initial plan. The new CT dataset should be used for IGRT image registration when the patient's shape changes significantly.

5.1.1.2 Compliance Criteria

Treatment breaks must be clearly indicated in the treatment record along with the reason(s) for the

treatment break(s). Treatment breaks, if necessary, ideally should not exceed 5 treatment days at a time and 10 treatment days total. Treatment breaks should be allowed only for resolution of severe acute toxicity and/or for intercurrent illness and not for social or logistical reasons. Any treatment break(s) exceeding 2 treatment days for reasons other than toxicity/illness will be considered a protocol deviation. The following define compliance:

- Overall RT treatment time:
 - ≤ 52 days (compliant)
 - > 52 days (non-compliant)
- Up to 57 days for non-medical reasons (such as holiday, machine breakdown) as determined by the treating radiotherapy physician.

Missed treatments due to holidays or logistic reasons can be compensated for by delivering an additional BID treatment during the week, OR treating on the Saturday or Sunday of that week, OR adding to the end of treatment. These additions will not be considered non-compliance.

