5.1.1.4 R.T. Quality Assurance Reviews

RTOG uses several approaches to ensure H&N IMRT quality assurance (QA) including H&N anatomic atlases, site and machine certification of H&N IMRT, and individual case reviews. The department QA committee will perform RT Quality Assurance Reviews for this trial.

Technical Factors, Localization, Simulation, and ImmobilizationPatients must have an immobilization device (e.g. Aquaplast mask) made prior to treatment planning CT scan. The treatment planning CT scan should be performed with IV contrast so that the major vessels of the neck are easily visualized. The treatment planning CT scan must be performed with the immobilization device and in the treatment position. Slice thickness should be 0.3 cm.

Treatment Planning/Target Volume: Planning Target Volumes (PTVs): In general, the PTV should not go outside of the skin surface; if it does exceed the skin surface, the application of bolus material over this portion of the PTV may be considered if it is judged clinically that the skin is at risk but is generally not recommended. In general, the CTV-to-PTV expansion (without IGRT) should not exceed 10 mm. In general, the CTV-to-PTV expansion (with IGRT) should not exceed 5 mm.

Definition of Normal Tissues/Organs at Risk (OARs): NOTE: Only the parts of the normal tissues/organs at risk outside the PTVs will be considered for dose optimization purposes.

Spinal Cord: The cord begins at the cranial-cervical junction (i.e. the top of the C1 vertebral body). Superior to this is brainstem and inferior to this is cord. The inferior border of the spinal cord is at

approximately T3-4 (i.e., just below the lowest slice level that has PTV on it). The spinal cord shall be defined based on the treatment planning CT scan. In addition, however, a Planning Risk Volume (PRV) spinal cord shall be defined. The PRV_{cord} = cord + 5 mm in each dimension. This is irrespective of whether or not IGRT is used.

Brainstem: The inferior most portion of the brainstem is at the cranial-cervical junction where it meets the spinal cord. For the purposes of this study, the superior most portion of the brainstem is approximately at the level of the top of the posterior clinoid. The brainstem shall be defined based on the treatment planning CT scan. In addition, however, a Planning Risk Volume (PRV) brainstem shall be defined. The PRV_{brainstem} = brainstem + 3 mm in each dimension.

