5.1.2 Drug therapy

All systemic therapies are considered standard of care, and toxicities and dose modifications will be made by the treating physician based on institutional standards. Drugs are commercially available and are not considered investigational.

Patients Receiving Cisplatin or Cetuximab with Concurrent Radiation Therapy (RT)

Patients who receive cisplatin, will receive 100 mg/m², administered intravenously every three weeks (with a three day window) as per institutional standard. Patients who receive cetuximab will receive a loading dose of 400 mg/m² given at least 5 days prior to radiation initiation and 250 mg/m² given weekly during radiation. Chemotherapy can be given either before or after the radiation therapy fraction that is given on the same day. If radiation is held for more than 2 days (for any reason), cisplatin may be held as well until radiation resumes. High dose cisplatin is a highly emetogenic regimen with significant incidence of delayed nausea and vomiting whereas cetuximab is less than that at Gen.. Institutional guidelines for anti-emetic regimens should be followed per physician preference and institutional guidelines. Supportive care guidelines will vary by drug type but are standardized at the Markey Cancer Center via standardized chemotherapy order sets and electronic medical record order entry for all patients.

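### Section 5 gives no single reproducible rule for how non-medical radiotherapy delay counts in the primary compliance endpoint

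*Combined protocol and SAP*

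**What the plan says.** Section 5.1.1.2 presents its criteria as the definition of compliance. A course of at most 52 days is compliant and a longer one is not. It then adds "Up to 57 days for non-medical reasons (such as holiday, machine breakdown) as determined by the treating radiotherapy physician". The next paragraph deals with missed fractions: "Missed treatments due to holidays or logistic reasons can be compensated for by delivering an additional BID treatment during the week", on a weekend day of that week, or by adding to the end of treatment. It concludes: "These additions will not be considered non-compliance". The section also requires the reason for every break to be recorded, and treats a break of more than 2 treatment days for anything other than toxicity or illness as a protocol deviation.

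Section 5.1.5 states the primary outcome. Radiotherapy, with any prescribed chemotherapy, must be completed without dose reduction and without a radiotherapy delay that takes treatment past 50 days. It mentions no non-medical allowance. Its opening words also refer to no delay of radiation and/or chemotherapy. Section 13.1 sends the reader to section 5 for the detailed definition without saying which subsection governs.

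On chemotherapy, Section 5.1.2 says: "If radiation is held for more than 2 days (for any reason), cisplatin may be held as well until radiation resumes".

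**The concern.** Treatment compliance is the primary endpoint, and the interim look after 13 beet root patients (Section 13.2) uses it too. Two analysts working from the same treatment records should reach the same verdict on every patient. Here they may not, for three reasons.

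- **Mixed causes.** The 57-day figure is a total. The text does not say whether all the time beyond 52 days must be non-medical, or whether any non-medical miss opens the extension. The treating physician decides.
- **Two limits.** One subsection excuses some non-medical delay; the other sets a shorter limit and excuses none.
- **Chemotherapy.** The plan does not say whether a cisplatin hold that merely follows a machine or holiday hold of more than 2 days counts as a chemotherapy delay.

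With 10 and 15 patients in the two strata, a few such calls would be visible in the reported rate.

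**Working it through.** **Inputs.** 30 to 35 fractions, five per week (5.1.1.1); limits of 52 and 57 days (5.1.1.2) and 50 days (5.1.5); 25 beet root patients, 10 on chemoradiation and 15 on radiation alone (13.2); exact 90% binomial intervals (13.3).

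**The plan's own figures.** The largest half-width of the Clopper-Pearson 90% interval over all possible counts is 27.76% at n=10, 22.81% at n=15 and 17.67% at n=25. Section 13.2 states 27.75%, 22.85% and 17.7%, so the stated precision reproduces.

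**Day count.** Assumptions: 35 fractions on weekdays, Monday start, first fraction on day 1, every missed fraction added at the end.

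| Missed treatment days | 0 | 1 | 2 | 3 | 4 | 5 | 6 | 7 |
|---|---|---|---|---|---|---|---|---|
| Last day | 47 | 50 | 51 | 52 | 53 | 54 | 57 | 58 |

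**Verdicts.** The open reading lets any non-medical miss raise the ceiling to 57. The cause-specific reading excuses only the non-medical part.

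| Course | Last day | 5.1.1.2, open | 5.1.1.2, cause-specific | 5.1.5 |
|---|---|---|---|---|
| 2 holidays | 51 | compliant | compliant | non-compliant |
| 4 toxicity days | 53 | non-compliant | non-compliant | non-compliant |
| 4 toxicity days + 1 holiday | 54 | can be compliant | non-compliant | non-compliant |
| 5 toxicity days | 54 | non-compliant | non-compliant | non-compliant |
| 5 toxicity days + 1 holiday | 57 | can be compliant | non-compliant | non-compliant |

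**Sensitivity to the assumptions.** On the open reading with 35 fractions, one holiday changes the verdict after 4-5 toxicity days (Monday to Wednesday start), 3-5 (Thursday) or 2-5 (Friday). With 30 fractions it takes 7-10 toxicity days, depending on the start day. If days are counted as elapsed, every figure drops by 1: the 4-day break then ends at 52 and is compliant from the outset, while the 5-day example still switches (53 to 56).

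**Effect on the rate.** One patient is 1/25 = 4 points, 1/15 = 6.7 points or 1/10 = 10 points.

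**Effect at the interim look.** Assume a uniform Beta(1,1) prior, since the plan names a non-informative prior without its parameters. The posterior probability that the rate is at most 52.17% is 0.67 with 6 of 13 compliant and 0.46 with 7 of 13.

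**The case against.** The strongest reply is that 5.1.1.2 can be read sensibly. Its 57-day line is tied to non-medical reasons, which may mean that the excess over 52 days must be non-medical. The sentence on make-up fractions then works like a credit, and the switch disappears. The examples given, holidays and machine breakdowns, are checkable events. Section 5.1.1 calls the radiotherapy guidelines recommended practice, so 5.1.5 may be meant to govern, and on that text every toxicity-delayed example fails anyway.

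Much of this stands, and it rules out several stronger readings that a reader might infer:

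- **A flat 57-day ceiling.** The text does not say the allowance is flat; that is one reading of two.
- **An upward bias.** This is not shown. Three toxicity days plus four logistic misses end on day 58 and fail under a 57-day cap, although the toxicity days alone end on day 52.
- **An unblinded assessor.** Section 9.5.1 describes the treating radiation oncologist as blinded for mucositis grading. That is hard to square with a non-randomized design, but the documents do not settle who knows what when delay is classified.
- **A contradiction between the 57-day cap and the excused additions.** The two fit together if additions are excused within the cap. BID or weekend make-up need not lengthen treatment, and long logistic breaks are already deviations.
- **A chemotherapy failure after a single holiday.** Section 5.1.2 applies only to holds of more than 2 days and is permissive.

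The reply does not remove the ambiguity. The plan does not choose between the readings of 5.1.1.2, or between that section and 5.1.5. Two holiday misses made up at the end get opposite verdicts from the two sections, with no toxicity involved.

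**Conclusion.** The point holds as an unresolved definition of the primary endpoint. Mixed-cause delay has no stated scoring rule, and Sections 5.1.1.2 and 5.1.5 can give opposite results for the same course. The switch from day 53 non-compliant to day 54 compliant arises only if 5.1.1.2 governs and is read openly. It also depends on the number of fractions, the start day, how days are counted and make-up at the end. How often such courses will occur cannot be estimated from the documents. Each one moves the rate by 4, 6.7 or 10 points, in a direction that is not established. The sponsor should settle this before analysis, and preferably before the interim look.

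**What to change.** 1. Reconcile 5.1.1.2 and 5.1.5. The sponsor chooses the limit and whether a cap on total time applies; this review takes no position on either. State how days are counted.
2. Before analysis, state one objective scoring rule for non-medical delay. For example, use the recorded break reasons to recompute the completion date as if fractions missed for documented non-medical reasons had been given on schedule, and apply the reconciled limit to that date. Subtracting missed treatment days from the total is not equivalent, because it ignores weekends. Three toxicity plus three holiday misses end on day 57, and 57 - 3 = 54, whereas the toxicity days alone end on day 52.
3. State whether a cisplatin hold that only follows a non-medical radiotherapy hold of more than 2 days counts as a chemotherapy delay.
4. Name who assigns the reasons. If the department QA committee is chosen, add the task explicitly: Section 5.1.1.4 gives it radiotherapy quality reviews but does not mention break reasons.
5. Report the compliance rate on actual elapsed days, with no credit, as a sensitivity result.

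The cost is a protocol clarification and a little extra coding from records already required. The reported rate may move either way. Treatment is unaffected.
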